6.2.2 Mode of Action

Copanlisib is a pan-class I phosphatidylinositol 3-kinase (PI3K) inhibitor with predominant and potent activity against the PI3K- δ and PI3K- α isoforms. The PI3K pathway is a

prominent pathway that promotes cellular survival and is found to be constitutively activated in many cancer types. Inhibition of this pathway is expected to lead to impaired cellular uptake of glucose, with a subsequent reactive rise in plasma insulin and glucose levels.

6.2.3 Description

Copanlisib is supplied as lyophilized preparation in a 6-mL injection vial. The total amount of BAY 80-6946 per vial is 60 mg. The solution for IV infusion is obtained after reconstitution of the lyophilisate with 0.9% sodium chloride solution.

6.2.4 Packaging and Labeling Information

Clinical supplies will be affixed with a clinical label in accordance with regulatory requirements. Open label kits will be provided for patient dosing.

This trial is open-label; therefore, the participant, the trial site personnel, the Sponsor and/or designee are not blinded to treatment. Drug identity (name, strength) is included in the label text.

6.2.5 Preparation

Refer to the Pharmacy Manual for preparation instructions.

6.2.6 Storage and Handling Requirements

Copanlisib must be stored between +2°C and +8°C and should not be transported above +30°C. Clinical supplies must be stored in a secure, limited-access location.

Receipt and dispensing of trial medication must be recorded by an authorized person at the trial site. Clinical supplies may not be used for any purpose other than that stated in the protocol.

6.2.7 Stability

Refrigeration is not required if reconstituted copanlisib is used immediately (within max of 4 hours). If not used immediately, store reconstituted solution in the vials or in the infusion bag at +2°C to +8°C (36°F to 46°F). Allow the product to adapt to room temperature after refrigeration. It takes approximately 60 minutes for a 100 mL dilution filled in bags to return to room temperature after refrigeration. The overall storage time must not exceed 24 hours including preparation and administration. Avoid exposure of the diluted solution to direct sunlight.

6.2.8 Route of Administration

Copanlisib is administered in a normal saline solution, intravenously, over 1 h. No intravenous glucose preparations should be administered on the days of infusion.

6.2.9 Returns and Reconciliation

The investigator is responsible for keeping accurate records of the clinical supplies received

from Bayer or designee, the amount dispensed to and returned by the participants and the amount remaining at the conclusion of the trial.

Upon completion or termination of the study, all unused and/or partially used investigational product will be destroyed at the site per institutional policy. It is the Investigator's responsibility to arrange for disposal of all empty containers, provided that procedures for proper disposal have been established according to applicable federal, state, local and institutional guidelines and procedures, and provided that appropriate records of disposal are kept.

7. CORRELATIVE/SPECIAL STUDIES

Detailed instructions for collection, processing, and storage of tumor and blood samples are provided in the Laboratory Manual. Results from the sequencing studies will not be released to the patients. These studies are for research purposes only and are not using a clinically validated platform.

7.1 Tumor Tissue

Patients in both phases of the study will have paired biopsies – one prior to treatment and one after six weeks on therapy (4-6 cores per time point). This will be prior to Cycle 2 Day 15 treatment, after two doses of nivolumab and three or five doses of copanlisib (depending on the dose level). Patients will also be asked for an optional biopsy at the time of progression.

Tumor biopsy will not be performed if the tumor is not accessible or if biopsy is considered not in the patient's best interest.

Attempts will be made to obtain archived tissue samples from all subjects. Archived FNA biopsy samples do not contain sufficient tissue and will not be collected.

We will assess tumor immune infiltrate using immunohistochemistry (IHC) and flow cytometry of disaggregated tumor samples. Expression of PD-L1 and of a series of biomarkers will be assessed by IHC. CD8+ T cells will be enriched by magnetic separation from disaggregated tumor samples and stimulated *ex vivo* to query markers of T cell exhaustion and cytokine production. We will also use single cell RNASeq for an unbiased assessment not only of cellular composition but also of functional status as assessed by gene expression profiles. From single cell expression data, we hope to identify gene expression profiles of tumor cells that are correlated with response to therapy.

Tumor Sample Requirements:

Slides

H&E

10 unstained FFPE

Tissue

50mg fresh (flow cytometry)

50mg fresh (*ex vivo* T cell stimulation)

25 mg fresh/frozen (single cell RNASeq)

7.2 Peripheral Blood Mononuclear Cells (PBMCs)

Up to 100 cc of whole blood for isolation of PBMCs will be collected at baseline prior to first dose of study drug, at 2 weeks after first dose, on Day 1 of each odd cycle, and at progression or EOT visit. Phenotypic and functional analysis of PBMCs via flow cytometry will be performed.

7.3 Plasma

Up to 20 cc whole blood for plasma will be collected at baseline prior to first dose of study drug, at 2 weeks after first dose, on Day 1 of each odd cycle, and at progression or EOT visit.

Peripheral Cytokines will be measured by standard luminex assays from patient plasma. We will measure cytokine levels from peripheral blood including but not limited to IFN γ , TNF α , TGF β , IL-10, CXCL9, CCL2, IL-6, IL-12, IL-2 and IL-17.

7.4 Diagnostic Tissue Samples

Tissue, fluid, or blood may be collected from standard of care procedures used to treat or diagnose immune-related toxicities.

7.5 Planned Analyses

7.5.1 PI3K mutation assessment

PI3K mutation assessment will be performed centrally in batched analysis using NGS and PCR based testing by a CLIA certified lab. All PI3K mutations will be noted, but the patient will be considered to have PI3K mutations if they have a known-activating mutation of PIK3 as defined in **Table 8**. Additional mutations may be added to this definition in the face of emerging discovery.

Table 8 – Activating PIK3 Mutations

G106R
R108H
P124L
V344G
N345K
C420R
E542K
E543 I459del
E545K, E545A, E545Q, E545G
Q546K
Q546R, Q546P
H1047R, H1047L
G1049R

7.5.2 Determining effect of copanlisib on tumor immune subpopulations.

Expected results include 1) an increase in the number of infiltrating CD8+ T cells following treatment with copanlisib and nivolumab and/or 2) a decrease in immunosuppressive cells including CD4+, FOXP3+ Treg cells or functional myeloid derived suppressor cells (MDSCs). Objectives related to tumor immune subsets will be accomplished by three techniques, and tissue prioritized as below. Intended comparisons are between paired biopsy specimens from the same patient, where a change in populations can be correlated with treatment, as well as inter-patient comparisons for correlation with clinical response.

1. Multiplex IHC/IF

A series of biomarkers will be assessed on tissue from this study. A sample of immune and other markers in **Table 9** will be the stains of high priority for these exploratory investigations, in order of priority based on amount and quality of tissue obtained. Briefly, tumor samples will be stained on a quantitative multiplex immunohistochemical platform developed at Johns Hopkins Sidney Kimmel Comprehensive Cancer Center that was previously published²². This technology incorporates a computational image processing workflow, including image cytometry, that enables simultaneous evaluation of 12 biomarkers in one formalin fixed paraffin-embedded tissue section. This platform is readily adaptable to assess a variety of markers including lymphoid and myeloid lineage markers, in addition to those listed in **Table 9**. After staining, slides will be analyzed in the Cell Imaging Core Facility at Johns Hopkins Sidney Kimmel Comprehensive Cancer Center to quantitate the percentage and intensity of cells for each marker(s) in the TME. The biomarker data will be captured for samples according to a digital image workflow. Briefly, this encompasses three steps: image preprocessing, visualization, and quantitative image analysis using state-of-the-art software in the Core Lab. This system allows for true quantitative data on dual staining in patient samples. These IHC and IF analyses will be conducted under the guidance of [REDACTED]. To ensure the rigor of these analyses, samples will be batch run when possible, with appropriate positive (i.e. tonsil tissue for immunostains) and negative controls (secondary Ab only) along with serial sections from a single archival colon carcinoma tumor specimen as a qualitative control to for intensity and any batch-to-batch variability between reagents used in IHC or IF assays.

Table 9 - Planned Immunohistochemical (IHC) and Immunofluorescence (IF) analysis (*denotes primary biomarker)

Immunohistochemistry	Immunofluorescence	
CD8*, CD4, PD-L1, PTEN	CD8+, Ki67+, CD8+Nur77+, CD4+FoxP3+	Priority 1
CD11c, CD19, CD68, CD163, CTLA4, PD-1, PD-L2, IDO1, LAG3, p-AKT	CD33+S100+, CD4+IL-17+	Priority 2

2. Flow cytometry

When adequate fresh tissue can be obtained, tumor will be disaggregated using a combination of enzymatic and mechanical disruption²³. Resulting suspension will be analyzed by flow cytometry with markers shown in **Table 10**. Included in this panel is analysis of a subset of CD8+ T cells identified by [REDACTED]

(CD8+Ki67+) that displays a proliferative burst after PD-1 blockade and may be a potential biomarker of response to anti-PD-1 therapy²⁴. Populations will be normalized to tumor weight using counting beads.

Table 10 - Planned markers for flow cytometry of disaggregated tumor biopsies.

Cell population	Marker
CD8+ T cell	CD8, GZMB, PD-1, Tim3, Lag3, 2B4, Ki67
Regulatory CD4+ FOXP3+ T Cell	CD4, FOXP3
MDSC	CD11b, HLA-DR, CD14, CD15, CD33, Lin-(CD3/14/15/19/56)
NK	CD56
B cell	CD19

3. Single cell/nuclei RNASeq

Single cell RNASeq will provide an unbiased assessment of cellular composition and of functional status as assessed by individual cell gene expression profiles. Single cell sequencing of tumor biopsies will be performed using droplet technology (10X genomics), whereby single cells from tumor suspensions are partitioned and a unique transcriptome barcode applied prior to lysis and whole transcriptome amplification. High-quality data will be generated from 6-10,000 tumor and immune cells from each biopsy. Each biopsy will contain both tumor, stromal and immune cells, which will allow the broadest analysis of the tumor microenvironment. Initial analysis based on signature enrichment will allow the deconvolution of tumor vs. non-tumor (stroma, immune cell) populations. Subsequent analyses will include reconstruction of TCR sequences and tracking of TCR clones throughout subpopulations²⁵, arrangement of cells in pseudotemporal space with Monocle²⁶, differential expression analysis based on mixture models to account for the zero-inflation of single cell transcriptional data²⁷, and calculation of cell-by-cell gene-set signature scores²⁸ to probe for pathway and phenotype-level differences between subpopulations.

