1.5 Study Design

This is a multi-center, open-label, Phase I/II study. Phase 1 consists of a 3+3 dose de-escalation design to determine the dose of copanlisib for use in combination with nivolumab. Approximately 6-18 subjects with solid tumors will be treated in Phase I and will be monitored for dose limiting toxicities (DLTs) through their first cycle of treatment. Complete information on the definition of DLTs and dose de-escalation rules can be found in **Section 4.3**.

The Phase II portion of the study will evaluate the safety and clinical activity of copanlisib and nivolumab in two cohorts of patients with previously treated metastatic colon cancer. Cohort A will enroll patients with PI3K mutation and Cohort B will enroll patients with wildtype PI3K status. Twenty-one patients are targeted for enrollment in each cohort, for an approximate total of 42 patients in Phase II. Enrollment in Phase II will be initiated once the recommended phase II dose (RP2D) has been determined in Phase I.

For all patients, the study will consist of a screening period, a treatment period, and a follow-up period. Screening evaluations will be done within 28 days prior to the start of study treatment.

Each treatment cycle is 28 days. Patients in both Phase I and Phase II will receive nivolumab on Day 1 of each cycle (every 4 weeks) and copanlisib on either Day 1, Day 8, and Day 15 of each cycle (3 week on, one week off) or on Day 1 and 15 of each cycle (every 2 weeks), depending on the dose level and RP2D. Complete information on study drug administration, schedule, and dosing can be found in **Section 4.2**.

Phase II enrollment will be carried out in 2 stages so that the study can terminate early if the combination of copanlisib and nivolumab is not sufficiently effective. In the first stage, 12 subjects will be accrued to each cohort. If there are no responders among the first 12 patients, the study will be terminated for futility. Otherwise, 9 additional patients will be accrued for a total of 21 treated subjects. If ≥ 3 out of the 21 patients have a response, then the trial will be considered a success for that cohort.

Clinical and immune responses will be evaluated at baseline and during treatment through tumor assessments, biopsies, and PBMC and plasma collection. Tumor assessments will be made using RECIST 1.1.

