3. PATIENT SELECTION

3.1 Eligibility Criteria

In order to be eligible for participation in this study, all of the following criteria must apply:

1. Be willing and able to provide written informed consent for the trial
2. Be at least 18 years of age on the day of signing informed consent
3. Have histologically confirmed metastatic or unresectable:
 - a. Mismatch-repair proficient (MSS) solid tumor (for phase I dose de-escalation)
OR
 - b. Mismatch-repair proficient (MSS) colorectal cancer with known PI3K-mutation status (for expansion cohorts). NGS and PCR based testing by a CLIA certified lab will be used to determine PI3K status per **Section 7.5.1**.
4. In terms of prior therapies:
 - a. For phase I dose de-escalation: have received all curative treatment options AND at least 2 lines of systemic therapy in the metastatic setting
 - b. For MSS colorectal cancer cohorts in phase II expansion: have received at least 2 prior lines of standard therapy including a fluoropyrimidine, oxaliplatin, and irinotecan-containing regimen. KRAS/NRAS/BRAF wild type patients must have received or refused anti-EGFR therapy.
5. Have measurable disease based on RECIST 1.1. Lesions situated in a previously irradiated area are considered measurable if progression has been demonstrated in such lesions.
6. Have biopsiable disease. If biopsy is attempted and unsuccessful (the patient undergoes an invasive procedure), the patient may still be treated.
7. Have a performance status of 0 or 1 on the ECOG Performance Scale at study entry (See Appendix A).
8. Have a life expectancy of 3 months
9. Demonstrate adequate baseline laboratory values as defined below; all screening labs should be performed within 21 days of treatment initiation.

System – Lab	Laboratory Value
Hematological	
Absolute neutrophil count (ANC)	$\geq 1500/\mu\text{L}$
Platelets	$\geq 75\,000/\mu\text{L}$
Hemoglobin	$\geq 8.0\text{ g/dL}$ or $\geq 5.6\text{ mmol/L}^{\text{a}}$
Renal	
Serum Creatinine	$\leq 1.5 \times \text{ULN}$ or Glomerular filtration rate (GFR) $\geq 40\text{ mL/min/1.73}$
Urine protein:creatinine ration (UPCR)	< 3.5 on a random urine sample
Hepatic/pancreatic	
Total bilirubin	$\leq 1.5 \times \text{ULN}$ ($< 2 \times \text{ULN}$ for patients with Gilbert's syndrome)
AST (SGOT) and ALT (SGPT)	$\leq 3 \times \text{ULN}$
Lipase	$< 1.5 \times \text{ULN}$
Endocrine	
HbA1c	$\leq 7\%$
Glucose	$< 160\text{ mg/dL}$ (fasting) or $< 200\text{ mg/dL}$ (non-fasting)
Coagulation	

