4.2 Agent Administration

There will be two phases in this study: A Phase I dose-finding stage followed by a Phase II expansion.

Copanlisib will be administered as a 60 minute IV infusion (-5min/+10min) at the doses and days shown in **Table 1** and **Table 2** below. Subjects should be observed for a minimum of 30 minutes after administration of Copanlisib prior to administration of nivolumab.

Nivolumab 480 mg will be administered as a 30 minute IV infusion (-5min/+10min) on Day 1 of each 28 day cycle.

The Pharmacy Manual contains specific instructions for the preparation and administration of these study drugs.

[figure not shown]
Study treatment should be administered after all procedures/assessments have been completed for that visit as detailed on the Study Calendar (**Section 8**). Study treatment may be administered up to 3 days before or after the scheduled Day 1 of each cycle, up to 1 day after the scheduled Day 8, or up to 3 days after Day 15 of each cycle due to administrative reasons as long as there is a minimum of 7 days between copanlisib infusions.

All trial treatments will be administered on an outpatient basis.

Phase I – Dose De-Escalation

Phase I will use a standard 3+3 design. The initial dose being tested is the recommended phase 2 dose of both study drugs as single agents, so the doses of copanlisib and nivolumab will not escalate higher than dose level 1. However, if the recommended phase II dose (RP2D) is exceeded in dose level 1, the dose of copanlisib will de-escalate as indicated below in Table 1. A maximum of 18 eligible subjects will be enrolled into this phase. All patients enrolled at each dose level will be evaluated for dose limiting toxicities (DLTs) during the first 28 day cycle for the purpose of determining the RP2D when given concurrently with nivolumab. DLTs and dose de-escalation rules are defined in **Section 4.3** and **Table 3**, respectively.

[figure not shown]
Table 1 – Phase I Dose Levels and Regimen (listed in order of administration)

Phase II – Expansion Cohorts

Phase II will enroll patients with mismatch-repair proficient colorectal cancer with known PI3K-mutation status. 21 patients will be enrolled into Cohort A (PIK3CA mutation) and 21 patients will be enrolled into Cohort B (PIK3CA WT). Both cohorts will receive the same treatment regimen. The dose of copanlisib given in Phase II will be the RP2D determined during Phase I of this study.

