11. STATISTICAL CONSIDERATIONS

11.1 Sample Size

Phase I will be enrolled in a standard 3+3 design with up to 18 patients. For the purposes of dose finding, DLTs will be evaluated during the first cycle for each patient. An initial cohort of 3 patients will be enrolled. If 0-1/3 have a DLT then 3 additional patients will be enrolled at the same dose level. If 2-3/3 DLTs are observed, then the dose will be considered too toxic and the next lower dose level will be enrolled. The RP2D is the dose at which $\leq 1/6$ patients have a DLT (i.e. if 0/3 of the initial patients have a DLT then an additional 3 will be recruited at the highest feasible dose to establish the RP2D).

During Phase II 42 patients will be recruited: 21 patients with colorectal cancer with PIK3CA mutation (cohort A) and 21 with WT PIK3CA with known lack of sensitivity to immune checkpoint inhibitor therapy (cohort B). ORR (CR+PR) at 6 months the primary endpoint and will be evaluated separately in each cohort. Enrollment will be carried out in 2 stages so that the study can terminate early if the combination of copanlisib and nivolumab is not sufficiently effective. A design similar to Simon's minimax design with relaxed futility stopping will be employed to test the null hypothesis that the true ORR is 5% or less.³⁰⁻³¹ In the first stage, 12 subjects will be accrued in each cohort. If there are no responders among the first 12 patients, the study will be terminated for futility. Otherwise, 9 additional patients will be accrued for a

total of 21 treated subjects. Patients who withdraw consent before disease re-evaluation will not be considered evaluable for response and may be replaced. Patients who come off of study prior to disease re-evaluation with imaging due to clinical deterioration will be considered evaluable for response and will be coded as progressing. If ≥ 3 out of the 21 patients have a response, then the trial will be considered a success for that cohort. If the true response rate is 20% (alternative hypothesis rate), then the probability of a declaring the treatment a success is 0.80 (power). If the true response rate is 5% (null hypothesis rate), then the probability of declaring the treatment a success is 0.08 (type I error).

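### Could adding variants to the Table 8 mutation list move treated patients between Cohorts A and B and distort the phase II error rates?

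*Combined protocol and SAP*

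**What the plan says.** Section 7.5.1 gives the classification rule: "All PI3K mutations will be noted, but the patient will be considered to have PI3K mutations if they have a known-activating mutation of PIK3", with the qualifying variants listed in Table 8. Other PI3K variants are recorded but do not make a patient mutant. The section then adds: "Additional mutations may be added to this definition in the face of emerging discovery". It names no cut-off date and no approval step, and it does not say whether an addition reaches back to patients already registered. It also says that "PI3K mutation assessment will be performed centrally in batched analysis".

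Elsewhere, cohort is treated as a property at entry. Criterion 3b in section 3.1 requires "colorectal cancer with known PI3K-mutation status (for expansion cohorts" and points to section 7.5.1 for the testing. Section 1.5 says that "Cohort B will enroll patients with wildtype PI3K status", and section 4.2 says that "21 patients will be enrolled into Cohort B (PIK3CA WT". Under section 4.1, eligibility is verified before the patient is registered.

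Section 11.1 judges each cohort separately: stop if none of the first 12 responds, otherwise continue to 21 and declare success at 3 or more responders. For a true response rate of 5% it states that "the probability of declaring the treatment a success is 0.08 (type I error"; for 20% it states a power of 0.80. Section 11.2 compares response between the cohorts by logistic regression.

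**The concern.** Cohort membership carries the whole of the phase II inference. It decides the stage 1 look, the success rule and the comparison of A with B. With a threshold of 3 responders, one patient can decide a cohort's result. The trial is open label and off-list variants are on record. Whoever extends Table 8 could therefore know which treated patients would move and whether they had responded.

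The stated error rates hold only if membership is settled without regard to outcome, and no sentence in sections 4.1, 7.5.1, 9.1, 11.1 or 11.2 says that a patient stays in the cohort of registration. If a responder moved, Cohort A could be judged on 22 patients and Cohort B on 20, sizes for which section 11.1 gives no rule. Prospective additions would be harmless; retrospective ones would not.

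**Working it through.** **Inputs.** From section 11.1: stage 1 of 12 patients, stop at 0; total 21; success at 3 or more; null rate 5%, alternative 20%. Assumed, because the documents give no figure: each Cohort B responder carries a later-added variant, and is moved to A, independently with probability q, where q is 2%, 5%, 10% or 20%. Also assumed: off-list carriers sit in Cohort B, the threshold stays at 3, and a 0/12 stop stands.

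**Step 1: the plan's own figures.** P(success) = Σ over x = 1 to 12 of P(Bin(12, p) = x) × P(Bin(9, p) ≥ 3 − x).
- p = 0.05: 0.0804 (stated 0.08). P(stop at 0/12) = 0.95^12 = 0.540.
- p = 0.20: 0.803 (stated 0.80).

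Both reproduce.

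**Step 2: how often one responder would matter.** At p = 0.05, P(pass stage 1 and end with exactly 2 of 21) = 0.164. One added responder would make this 3/22. A single-stage rule of 3 or more in 22 has type I error 0.095, against 0.085 for the single-stage rule in 21.

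**Step 3: both cohorts under relabelling.** With both true rates at 5%:
- Cohort A succeeds if it passes stage 1 and its own responders plus those moved in total at least 3.
- Cohort B succeeds if it passes stage 1 and at least 3 responders remain after the moves.

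The last column takes Cohort B alone, with a true rate of 20%.

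| q | P(at least one moved) | A false success | B false success | Sum | B power at 20% |
|---|---|---|---|---|---|
| 0 | 0 | 0.080 | 0.080 | 0.161 | 0.803 |
| 2% | 0.016 | 0.083 | 0.077 | 0.160 | 0.792 |
| 5% | 0.039 | 0.087 | 0.071 | 0.158 | 0.775 |
| 10% | 0.076 | 0.094 | 0.063 | 0.157 | 0.742 |
| 20% | 0.144 | 0.108 | 0.047 | 0.155 | 0.665 |

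Cohort A's gain is Cohort B's loss. The expected number of false successes over the two cohorts does not rise.

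**Step 4: the A-versus-B comparison.** As an illustration with Fisher's exact test, suppose both cohorts end at 2/21 (p = 1.00). Moving one responder gives 3/22 against 1/20, p = 0.61. One move does not create a difference between cohorts.

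**Step 5: what the text implies about timing.** Criterion 3b makes status a condition of entry. Sections 1.5 and 4.2 define the cohorts by enrolment, and section 4.1 puts the eligibility check before registration. Section 7.5.1 lets the list grow but does not say that earlier assignments are reopened. Read together, a patient's cohort is the one that applied at registration.

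**The case for a change.** The strongest argument is that an entry requirement does not freeze the definition used in the analysis, and that section 7.5.1 expressly allows this definition to change. A list extended after responses are known, by people who know which patients would be affected, is a recognised route to a biased result, and a short statement would close it. It is true that no such statement exists. Version control helps only in part: the protocol carries dated versions, and section 10.1 makes the Protocol Chair responsible for having amendments approved and for sites using the correct version, but section 7.5.1 does not say that an addition needs an amendment.

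The table also does not measure deliberate, outcome-driven relabelling. It moves patients by variant alone, and Cohort A's rise comes from letting that cohort exceed 21 patients at an unchanged threshold. Selective moves could do more harm, but they would need a use of section 7.5.1 that the plan does not describe. The loss of power in Cohort B is real in the model, yet it is large only at the upper shares. Table 8 already lists 18 variants, and the documents give no reason to expect 10% or 20% of Cohort B responders to carry one that is both off the list and added later.

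Two side points do not add a separate defect. Carriers of off-list variants are not mutant under section 7.5.1, so with two cohorts they fall in B, despite the looser wild-type label. Central batched testing does not contradict criterion 3b, which refers to that same testing and still requires the status to be known.

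**Conclusion.** The concern does not call for a change. It identifies a missing clarifying sentence, which an analyst would fill sensibly by using the cohort assigned at registration. Followed in that way, the design has the stated properties: type I error 0.0804 and power 0.803 per cohort.

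Even if variants recognised through outside discovery were applied backwards, the assumed range of 2% to 20% puts Cohort A's false-success probability at 0.083 to 0.108 and Cohort B's at 0.077 to 0.047. Their sum is 0.160 to 0.155, against 0.161 with no moves. Cohort B's power at a 20% response rate would be 0.792 to 0.665.

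These figures rest on independent responses, relabelling by variant and not by outcome, a threshold kept at 3, and a 0/12 stop that stands. Real harm needs retroactive, outcome-driven reassignment, which the documents neither plan nor imply.
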